4. CHANGES IN THE PLANNED ANALYSIS OF THE STUDY

The following further categorical endpoints were added:

5. ENDPOINT(S)

5.1 PRIMARY ENDPOINT(S)

The primary focus is on safety endpoints. Please refer to CTP Section 2.1.2.

5.2 SECONDARY ENDPOINT(S)

5.2.1 Key secondary endpoint(s)

Not applicable.

5.2.2 Secondary endpoint(s)

Not applicable.

5.4 OTHER VARIABLE(S)

5.4.1 Demographics and baseline characteristics

Demographics and other baseline characteristics will include the following.

5.4.1.1 Demographic data

- Gender
- Race (as collected in parent trial): single race respondents, multiple race respondents (all combinations ticked), and all race categories regardless of how many race categories were ticked
- Ethnicity (as collected in parent trial)
- Age [years] will be calculated as: year of informed consent in extension trial 1199.225 - year of birth
- Age in classes [years] (<30; >=30 to <45; >=45 to <60; >=60 to <75; >=75)
- Age at randomisation in parent trial [years] (as derived in the parent trial CRF as year of informed consent in parent trial - year of birth)
- Age at randomisation in parent trial in classes [years] (<30; >=30 to <45; >=45 to <60; >=60 to <75; >=75)
- Weight [kg] (at inclusion in extension trial 1199.225) as continuous variable and in classes (<30; ≥30 to <60; ≥60 to <90; ≥90)
- Height [cm] (at inclusion in extension trial 1199.225)
- Body mass index [kg/m²], at inclusion in extension trial 1199.225: Weight [kg] / Height [m] * Height [m], as a continuous variable and in classes (< 18.5; >=18.5 to <25; >=25 to <30, >=30)

5.4.1.2 Other baseline characteristics

The following baseline efficacy variables and SSc characteristics will be summarised for the parent trial:

- FVC in mL and in % predicted at randomisation
- Modified Rodnan Skin Score (mRSS)
- Digital ulcers count and net burden [fingers]
- SGRQ Total, Symptoms, Activities and Impact scores
- Time since first onset of non-Raynaud symptom [years]
- Time since first onset of Raynaud symptom [years]
- Time since first diagnosis of SSc-ILD [years]
- SSc subtype (diffuse cutaneous SSc, limited cutaneous SSc)
- ATA status (positive, negative)

5.4.2 Compliance

Compliance (%) at each visit is collected in the eCRF and will not be recalculated. An overall compliance will be calculated as a time-weighted average over all visits. Each weight will be based on the number of days between the compliance measurement and the previous one (or the date of first trial drug intake for the first compliance measurement). If compliance is missing for at least one expected visit then overall compliance will be missing.

Likewise, compliance will be calculated at 1 year (up to 52 weeks [Visit 7]), at 2 years (up to 100 weeks [Visit 10]), and at each year (based on data collected every 48 weeks).

Overall and annual compliance will be summarised and categorised into classes: <50%, >=50% to <80%, >=80% to <= 120%, > 120%.

5.4.3 Exposure

Exposure will be calculated during 1199.225 extension trial. The date of first trial drug intake is recorded at visit 2.

- Duration of exposure [months] = (Date of last trial drug intake– date of first trial drug intake in extension trial 1199.225 +1 day) /30.5. Treatment interruptions will not be subtracted from this duration of exposure.
- Duration of exposure in categories: <= 3 months (91 days); > 3 months (91 days) to <= 6 months (182 days); > 6 months to <= 12 months (365 days); > 12 months to <= 18 months (547 days); > 18 months to <= 24 months (730 days); > 24 months to <=36 months (1095 days); > 36 months to <=48 months (1460 days); > 48 months to <=60 months (1825 days); > 60 months to <=72 months (2190 days); >72 months
- Duration while 150 mg bid actually taken [months]: Sum of each continuous duration of exposure to 150 m bid [days] /30.5. This duration of exposure will be adjusted for treatment interruptions, dose reductions and dose increases.

- Duration while 100 mg bid actually taken [months]: Sum of each continuous duration of exposure to 100 mg bid [days] /30.5. This duration of exposure will be adjusted for treatment interruptions, dose reductions and dose increases.
- Total dose [g]: Duration while 150 mg bid actually taken [days] * 0.3 g + duration while 100 mg bid actually taken [days] * 0.2 g.
- Dose intensity [%]: $\text{Total dose [g]} * 100 / \{0.3g * (\text{Duration of exposure [days]})\}$
- Dose intensity in categories: $\leq 30\%$, $>30\%$ to $\leq 50\%$, $>50\%$ to $\leq 90\%$, $>90\%$ to $<100\%$, $\geq 100\%$.

5.4.4 Liver enzyme and bilirubin elevations

Liver enzyme and bilirubin elevations will be reported using the following definitions:

- (ALT and/or AST ≥ 3 fold ULN) AND bilirubin ≥ 2 fold ULN^[1]
 - And ALK ≥ 2 fold ULN^[1]
 - And ALK < 2 fold ULN^[1]

^[1] These elevations are defined within a time window of 30 days i.e. the elevation of bilirubin should appear within 30 days after the elevation of AST and/or ALT.

- ALT ≥ 5 fold ULN and/or AST ≥ 5 fold ULN
- ALT ≥ 3 fold ULN and/or AST ≥ 3 fold ULN
- ALT ≥ 1.5 fold ULN and/or AST ≥ 1.5 fold ULN

[figure not shown]
The proportion of patients presenting signs of hepatic injury will be summarised, based on the following definition for signs of hepatic injury:

- ALT and/or AST ≥ 8 fold ULN
- ALT and/or AST ≥ 3 fold ULN and total bilirubin ≥ 2 fold ULN in the same sample
- ALT and/or AST ≥ 3 fold ULN and unexplained INR > 1.5 in the same sample
- ALT and/or AST ≥ 3 fold ULN and unexplained eosinophilia ($>5\%$) in the same sample
- ALT and/or AST ≥ 3 fold ULN and appearance of fatigue, nausea, vomiting, right upper abdominal quadrant pain or tenderness, fever and/or rash within +/- 7 days of the abnormal ALT and/or AST laboratory test result (please refer to [Section 9.2](#) for the list of relevant MedDRA preferred terms to support the derivation of a potential hepatic injury)

In addition, maximum individual elevations based on worst value on treatment will be defined as:

- ≥ 1.5 fold ULN; ≥ 3 fold ULN; ≥ 5 fold ULN; ≥ 8 fold ULN for AST and ALT
- $\geq 1.5 \times \text{ULN}$; ≥ 2 fold ULN for Bilirubin
- $\geq 1.5 \times \text{ULN}$; ≥ 2 fold ULN for ALK
- $\geq 1 \times \text{ULN}$; ≥ 3 fold ULN for GGT

Note: ULN refers to the Upper Limit of Normal from the Central Laboratory analyzing samples from this extension trial.

5.4.6 Safety time-to-event analyses

- Time to first dose reduction [days]
- Time to first treatment interruption [days]
- Time to permanent treatment discontinuation [days]
- Time to first dose reduction or treatment interruption [days]
- Time to first liver enzyme elevation (ALT and/or AST ≥ 3 xULN).

6. GENERAL ANALYSIS DEFINITIONS

6.1 TREATMENT(S)

For treatment specifications, see Section 4 of CTP.

The different periods of interest, as per CTP flow chart, are the following:

Note: the last day of each of the periods is excluded from the period. It defines the first day of the subsequent period.

- Previous trial:
 - If date of informed consent in 1199.225 and first trial drug intake in 1199.225 occur after or on last trial drug intake in SENCIS plus 28 days plus one day or date of trial completion in parent trial (SENCIS or 1199.340) plus one day, then previous trial period is defined as:

from informed consent in parent trial to the last trial drug intake in SENCIS plus 28 days plus one day or to the date of trial completion in parent trial (SENCIS or 1199.340) plus one day, whichever occurs later
 - If date of informed consent in 1199.225 or first trial drug intake in 1199.225 occur before last trial drug intake in SENCIS plus 28 days plus one day or date of trial completion in parent trial (SENCIS or 1199.340), then previous trial period is defined as:

from informed consent in parent trial to date of informed consent in 1199.225
- Between-trials (optional^[a]): from end of previous trial period (see above) to date of informed consent in 1199.225
- Screening (optional^[a]): from date of informed consent in 1199.225 to first trial drug intake in 1199.225
- Treatment period: from first trial drug intake in 1199.225 (or re-start of treatment if interruption) to last trial drug intake (or date of interruption if interruption) plus one day
- Off-treatment (optional^[a]): from date of start of interruption to re-start of treatment
- Residual effect period: from the last trial drug intake plus one day to last trial drug intake plus 7 days plus one day
- Follow-up (optional^[a]): from last trial drug intake plus 7 days plus one day (after residual effect period) to date of last contact as collected in the end of study CRF page plus one day. This period is only created if last trial drug intake took place more than 7 days before the last contact as collected in the end of study CRF page.

- Post-study: from the last trial drug intake plus 7 days plus one day to database lock or from the date of last contact as collected in the end of study CRF page (after follow-up period) plus one day to database lock, whichever occurs later

[a] This period is optional insofar as it does not necessarily exist for all patients.

For safety analyses ([Section 7.8](#)), data from the treatment period, possible off-treatment periods and residual effect period will be considered as on-treatment.

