#### **4.2 OTHER TREATMENTS, EMERGENCY PROCEDURES, RESTRICTIONS**

##### **4.2.1 Other treatments and emergency procedures**

Rescue medications to reverse the action of nintedanib are not available.

Dose reduction (from 150 mg bid to 100 mg bid) or treatment interruption should be considered to manage adverse events. No further dose reduction is possible for patients on the 100 mg bid dose. In case of persistent adverse events observed at this dose, or severe effects at 150 mg bid, permanent treatment discontinuation should be considered.

Treatment interruption and reduction and reescalation are repeatedly possible.

Table 4.2.1: 1 Allowed treatment reduction / interruption periods:

	AEs considered drug related	AEs or other events not considered drug related
Maximum interruption	4 weeks	12 weeks
Recommended restart	with reduced dose (100 mg bid)	with the same dose (100 mg bid or 150 mg bid)
Re-escalation	Any time to 150 mg bid	----

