7.8.1 Adverse events

Unless otherwise specified, the analyses of adverse events will be descriptive in nature. All analyses of AEs will be based on the number of subjects with AEs and NOT on the number of AEs.

For analysis multiple AE occurrence data on the CRF will be collapsed into an AE provided that all of the following applies:

- All AE attributes are identical (LLT, intensity, action taken, therapy required, seriousness, reason for seriousness, relationship [investigator defined drug-relatedness], outcome, AE of special interest).
- The occurrences were time-overlapping or time-adjacent (time-adjacency of 2 occurrences is given if the second occurrence started on the same day or on the day after the end of the first occurrence).

For further details on summarisation of AE data, please refer to [\(2,3\)](#).

The analysis of adverse events will be based on the concept of treatment emergent adverse events. That means that all adverse events occurring between first drug intake in extension trial till last drug intake + 7 days will be assigned to the on-treatment period and described according to randomised treatment in parent trial. All adverse events occurring before first drug intake will be assigned to 'previous trial', 'Between-trials' or 'screening'.

All adverse events occurring after the last trial drug intake will be assigned to 'residual effect period' or 'follow-up' or 'post-study' (for listings only). For details on the treatment definition, see [Section 6.1](#).

According to ICH E3 (4), AEs classified as 'other significant' needs to be reported and will include those non-serious and non-significant adverse events with

- (i) 'action taken = drug withdrawn' or 'action taken = dose reduced', or
- (ii) marked haematological and other lab abnormalities or lead to significant concomitant therapy

An overall summary of adverse events will be presented by randomised treatment in parent trial (and Total).

The frequency of patients with AEs will be summarised by randomised treatment in parent trial (and Total), primary system organ class (SOC) and preferred term (PT). This will be presented using a >5% cut-off in the CTR and repeated without the cut-off in the CTR appendices.

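### An adverse event with onset more than 7 days after the last dose before an interruption is on-treatment only if the patient later restarts, so serious and fatal events with such an onset that prevent a re-start are left out of the on-treatment SAE, fatal-AE and rate tables.

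*SAP*

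**What the plan says.** SAP 6.1 divides each patient's time into periods. An interruption creates an off-treatment period that runs "from date of start of interruption to re-start of treatment"; no other end point is given. The residual effect period runs "from the last trial drug intake plus one day to last trial drug intake plus 7 days plus one day". Because the section excludes the last day of every period, that means days 1 to 7 after the last intake. Follow-up runs "from last trial drug intake plus 7 days plus one day (after residual effect period) to date of last contact", and post-study comes after it. For safety analyses, "data from the treatment period, possible off-treatment periods and residual effect period will be considered as on-treatment".

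SAP 7.8.1 treats as treatment-emergent "all adverse events occurring between first drug intake in extension trial till last drug intake + 7 days". SAP 7.8.1.5 ends time at risk, for a patient without the event, at last intake plus 7 days or database lock, whichever is earlier. Interruptions are not subtracted.

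Protocol 7.3.4 sets the same window, assigns events by onset and uses a 7-day residual effect period. Protocol 5.2.11.2 still gives 28 days.

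On interruptions, Protocol 4.2.1 says: "Treatment interruption and reduction and reescalation are repeatedly possible". Its Table 4.2.1:1 sets maximum lengths of 4 weeks for drug-related adverse events and 12 weeks for other events. Protocol Appendix 10.3 adds interruptions when remote visits or liver monitoring cannot be done.

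**The concern.** The label given to an event in the later part of an interruption depends on something that happens afterwards: whether the patient goes back on drug. The event itself can decide that. If two patients each have a new serious event starting on day 20 of an interruption, the one who recovers and restarts has an on-treatment SAE. The one who does not restart has a follow-up or post-study event.

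Any error runs in one direction. The rule can remove late-interruption events of patients who did not restart, but never those of patients who did. In the rate tables, the restarters' interruption days stay in the denominator, while restart-preventing events from the same part of an interruption are missing from the numerator.

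Safety is the trial's main objective and every analysis is descriptive, so the SAE, fatal-AE and rate tables are its principal results. Interruptions longer than 7 days are foreseen by the protocol, so the case is not exotic.

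**Working it through.** The plan states no figure on this point to reproduce. The check applies the period rules and then counts days.

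**1. Classification.** Count days from the last dose before the interruption (day 0), and let R be the day of re-start, if any.

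| Onset of the AE | Patient restarts on day R | Patient never restarts |
|---|---|---|
| Day 0 or earlier | treatment period: on-treatment | treatment period: on-treatment |
| Days 1-7 | off-treatment period: on-treatment | residual effect period: on-treatment |
| Day 8 to R-1 (right column: day 8 onward) | off-treatment period: on-treatment | follow-up or post-study: not on-treatment |

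SAP 7.8.1 gives the same result. For a restarter the last intake comes after the interruption, so the whole interruption lies inside the window. For a non-restarter the last intake is day 0 and the window shuts after day 7.

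**2. Days on which the labels differ.** With re-start on the last permitted day, these are days 8 to R-1, that is R-8 days out of R-1.
- R = 28 (4 weeks): days 8-27, 28 - 8 = 20 of 27 days (74%).
- R = 84 (12 weeks): days 8-83, 84 - 8 = 76 of 83 days (92%).

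With the 28-day residual effect period of Protocol 5.2.11.2, the labels differ only from day 29. There is no such day when R = 28, and when R = 84 it is days 29-83, 83 - 28 = 55 days.

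These are shares of calendar days in a maximum-length interruption, not shares of events.

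**3. Rates: an illustration on assumed inputs.** The documents give no interruption or event rates. Assume 100 interruptions of planned length R, a proportion p with a new event that prevents re-start, and onset uniform over the interruption. Only interruption time is counted.
- Events counted under the plan: 100p x 7/R.
- Days at risk under the plan: 100(1-p)R, plus about 4 days per counted event and 7 days per uncounted one.
- Days at risk if all events count: 100(1-p)R + 100p x R/2.

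For p = 0.05 and R = 28:
- Plan: 5 x 7/28 = 1.25 events in 2660 + 1.25 x 4 + 3.75 x 7 = 2691.25 days, or 17.0 per 100 patient-years.
- All events: 5 events in 2660 + 5 x 14 = 2730 days, or 66.9 per 100 patient-years.
- Ratio: 0.25.

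Over p = 2% to 10% the ratio is 0.25 to 0.26 for R = 28 and 0.08 to 0.09 for R = 84. This covers restart-preventing events within interruptions only. Whole-trial rates would be diluted by all other events and person-time, by an amount that the documents do not allow one to compute.

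**The case against.** The strongest case against has five parts.

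- **Last dose plus 7 days is the protocol's own window and a conventional one.** True, and the main tables should keep it. The difficulty is combining it with whole interruptions for restarters only. If events more than 7 days off drug are not relevant (Protocol 1.2 gives a half-life of 7 to 19 hours), the restarters' late events are not relevant either. If they are relevant, the non-restarters' events are too.
- **Deaths.** A reader might infer that no death after day 7 of an interruption can be counted. The documents do not support that. Protocol 7.3.4 assigns by onset, so a fatal event that began before the interruption, or within 7 days of the last dose, counts whenever death occurs. A fatal event starting on day 20 in a patient who restarts and later dies of it also counts.
- **Primary endpoint.** A reader might infer that it is materially biased. It is the number and percentage of patients with any adverse event, and each patient counts once. A patient who interrupted because of an on-treatment event is already included. The SAE tables are also per patient, so an earlier on-treatment SAE keeps that patient in the overall SAE count.
- **Loss from the report.** A reader might infer that these events disappear altogether. That is not established. They remain in listings, and the SAP 7.8.1 restriction to listings may apply to post-study events alone. Protocol 7.5 mentions survival with censoring, and parts of the SAP are redacted, so deaths may be shown elsewhere.
- **The 7-day versus 28-day conflict.** It overlaps with this point but does not absorb it. A 28-day period removes the problem for 4-week interruptions and leaves it beyond day 28 of a 12-week one.

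These arguments limit the point. None removes the dependence on re-start.

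**Conclusion.** The point holds in a limited form. On the visible text of SAP 6.1, 7.8.1 and 7.8.1.5, an adverse event with onset on day 8 or later of an interruption is on-treatment only if the patient restarts. No visible passage corrects this for serious or fatal events. The outputs affected are the on-treatment SAE, fatal-AE and incidence-rate tables, and for restart-preventing events the direction is toward understatement.

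The number of patients affected is unknown. It depends on how many interruptions never end in a re-start and how many new serious or fatal events begin late in them. The day counts assume maximum-length interruptions and the SAP's 7-day residual effect period. The rate ratios also rest on the assumed event proportions and uniform onset, and should not be read as estimates for this trial.

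**What to change.** Keep the protocol's treatment-emergent window for the main tables.

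- **Add one analysis.** In SAP 7.8.1 and 7.8.1.5, for SAEs and for AEs leading to death, add an incidence and rate table of all events with onset from first extension dose to last contact, regardless of re-start. Time at risk should run to the same end point, or to first onset if earlier.
- **State the dependence.** Say in the report that the main on-treatment tables classify events during interruptions by whether the patient later restarted.
- **Optional sensitivity analysis.** Cutting every interruption at 7 days after the most recent dose treats restarters and non-restarters alike. It should not replace the main definition: it departs from Protocol 7.3.4 and can only leave the main counts unchanged or lower them.
- **Reconcile the residual effect period.** Protocol 5.2.11.2 (28 days) and Protocol 7.3.4 with SAP 6.1 (7 days) need to agree, since the affected days depend on it.

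The cost is one extra set of outputs, programmed from dosing, onset and last-contact dates already collected. The added table will include some events well after the last dose, and its title should say so. The point concerns analysis classification only; nothing here bears on the clinical rules for interrupting treatment.

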6.2 IMPORTANT PROTOCOL DEVIATIONS

As there is no Per Protocol Set planned in this trial, none of the iPDs will lead to exclusion from a patient set. However the proportion of patients with iPDs will be presented for completeness purposes and to demonstrate the adherence to the CTP.

Table 6.2: 1 Important protocol deviations

Category/Code	Description	Requirements	Excluded from
A	Entrance Criteria Not Met		
A1	Inclusion criteria not met		
A1.7	Parent study not completed	Inclusion criteria 1 not met (or trial drug prematurely discontinued according to CRFs data) Automatic IPD	None
A2	Exclusion criteria met		
A2.1	Patient has laboratory values that indicate additional risk: a) >3xULN for AST/ALT b) >2xULN for Bilirubin c) Creatinine clearance < 30 mL /min (Cockcroft-Gault formula)	Laboratory values out of range or missing at entry in the trial (visit 1 or visit 2) according to the database Automatic IPD	None
A2.2	Patient with other disease(s) which are excluded as per exclusion criteria	At least one of exclusion criteria 4, 5, 6, 7, 10, 12 met Automatic IPD for exclusion criteria 4, 6, 7, 10, 12 and manual for exclusion criterion 5	None
A2.3	Forbidden previous therapy	Exclusion criteria 5, 9 Manual IPD based on exclusion criteria and / or to be identified at the site level on the manual PD log	None

Table 6.2: 1 Important protocol deviations (cont'd)

Category/Code		Description	Requirements	Excluded from
	A2.4	Potential risk related to fetotoxicity	Inclusion criteria 3 not met or exclusion criteria 13 met Automatic IPD	None
	A2.5	Time period between parent trial and Visit 2 not observed	Exclusion criteria 8 met AND (time period > 12 weeks, i.e. ≥13 weeks between last trial drug intake of 1199.214 and Visit 2 of this study according to CRFs data or time period > 1 week, i.e. ≥2 weeks between last trial drug intake of 1199.340 and Visit 2 of this study) Automatic IPD	None
	A2.6	Any condition that makes them an unreliable trial subject or unlikely to complete the trial	Exclusion criteria 11 met Automatic IPD	None
	A2.7	Previous enrolment in this trial	Exclusion criteria 14 met Automatic IPD	None
B		Informed Consent		
	B1	Informed consent not given	Inclusion criteria 2 not met Automatic IPD	None
	B2	Informed consent given too late	CRF date of informed consent is after date of Visit 1. Signature of the wrong Informed Consent version, and later signature of the correct one will also be part of this IPD category Manual IPD	None
	B3	Informed consent not given or withdrawn for biobanking but biobanking done	According to database and CRF page informed consent for biobanking Automatic IPD	None
C		Trial medication and randomisation		
	C1	Incorrect trial medication taken	Wrong medication number. Medication kit assigned at visit 2 does not match treatment dose actually received by patient Automatic IPD	None
	C2	Trial medication not interrupted (or interruption done too late) when ALT or AST ≥ 5 fold ULN	Based on liver enzyme elevation and interruptions reported during the trial Manual IPD	None

Table 6.2: 1 Important protocol deviations (cont'd)

Category/Code	Description	Requirements	Excluded from
C3	Trial medication not permanently discontinued after signs of liver enzyme elevations were observed that a) are indicative of hepatic injury as defined in Section 5.4.4 b) correspond to ALT or AST \geq 3 fold ULN despite dose reduction or treatment interruption for 2 weeks or more	All patients where signs of liver enzyme elevations are not dealt with according to the requirements of the CTP and no confirmed alternative cause found (as confirmed by BI medicine) for the potential drug-induced liver injury (DILI) event. Manual IPD based on review of MORM listings	None
D	Concomitant Medication		
D1	Patient received prohibited concomitant therapies (see Section 4.2.2.1 of the CTP)	Investigational therapies are not allowed Review of MORM listings and / or to be identified at the site level on the manual PD log.	None
E	Missing data		
E1	Patient without any physical assessment for more than 6 months although under study medication	Prior to the start of COVID-19 disruption, no vital signs $>$ 6 months. After the start of COVID-19 disruption, no vital signs or local labs $>$ 6 months. Manual IPD	None
E2	Flow chart not observed for the planning of visit 1 and 2	Visit 1 and Visit 2 occurred on the same date whereas the period between last available laboratory test within SENCIS™ or 1199-0340 and Visit 2 of the extension trial (1199.225) is $>$ 6 weeks (i.e. \geq 7 weeks) Automatic IPD	None

